#### **Inclusion criteria**

##### **Patients:**

- 1) Must be 55 years old or older.
- 2) May be new, regular, emergency patients attending the TUKSoD clinic at Kleinlife or clinics at the Dental School or utilizing medical and social services at Kleinlife who have the intention to become patients of record at the dental clinic.

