#### **Study Procedure**

This will be a multi-center parallel group study with randomization to one of three arms as described below. The objective of this study is to test the efficacy of an oral health education group based activity versus an individual based oral health education activity in terms of changes in oral health related quality of life

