## ORAL HEALTH EDUCATION SENIORS

(OHRQoL), and self-efficacy among seniors at Kleinlife and at the Dental School. A description of the activities to be conducted in the intervention and control groups is described below:

Seniors who consent to participate in the study will be randomly allocated to one of the 3 following groups. Randomization will be determined according to a predetermined random sequence, and neither the patient nor the research staff will be aware of the randomization outcome until after the patient has agreed to participation.

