## ORAL HEALTH EDUCATION SENIORS

study:

- Oral Health Related Quality of Life: The Short-Form Oral Health Impact Profile (OHIP-14; Slade, 1997) is a 14-item self-report measure that assesses individuals' perceptions of the social impact of oral conditions on their well-being. This scale evaluates the consequences of oral conditions across dimensions of functional limitation, physical pain, psychological discomfort, physical disability, psychological disability, social disability, and handicap. Items are rated on a 5-point Likert-type scale ranging from 0 (*never*) to 4 (*very often*), regarding how frequently impact has been experienced. The total score ranges from 0 to 56; higher OHIP-14 scores indicate greater impact, hence poorer oral-health-related quality of life. The OHIP-14 has been validated in two national surveys of populations in the UK and Australia (Kelly et al., 1998; Steele et al., 2004) and demonstrated good reliability, construct and discriminant validity, and internal consistency (Slade & Spencer, 1994; Slade, 1997).
- Self-efficacy will be assessed based on a modified version of an instrument developed by Finlayson and colleagues (Finlayson et al, 2007). It will be measured using a 6-item scale, asking participants to indicate how confident they feel about their ability to brush their teeth at night when they were: (1) under a lot of stress; (2) depressed; (3) anxious; (4) feeling that they were too busy; (5) tired or; (6) worried about other things in their life. The four response options range from 'very confident' to 'not at all confident'. The possible score range is 0 to 24, with high scores indicating high self-efficacy. Alpha was 0.91. Self-efficacy will be dichotomized based on a median split, with low self-efficacy pertaining to scores of 0 to 11 and high self-efficacy pertaining to scores of 12+.
- Oral Health Knowledge: A 15-item questionnaire with a three-point Likert Scale (yes, no, and don't know) will be used to assess the oral health information/knowledge of the seniors pre and post intervention. Its respective psychometric properties (validity and reliability) have already been reported (Khanagar et al, 2014).
- Demographic Factors Questionnaire will identify key demographic factors such as age, sex, race, ethnicity, education and income level of seniors.

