### **Data Analysis:**

Initial analyses will be conducted to determine normality of distributions of the continuous variables, and any necessary transformations will be conducted. Primary outcomes will be the OHIP 14 and the self-efficacy scores. All eligible patients will be randomly assigned to 1 of the 3 groups described above. Although randomization should provide relatively comparable groups, demographic variables that differ between groups and are correlated with the primary outcomes will be used as covariates. Preliminary analysis will include measures of central tendency and dispersion, as well as an examination of the bivariate relationships among the primary and secondary outcome variables, potential moderators, and demographic characteristics.

Differences between the groups on baseline demographic, and psychological measures will be examined using  $\chi^2$  (Pearson) or Student's *t*-tests, as appropriate. Moreover, differences on the variables listed above among completers and drop-outs will also be explored. Intention to treat (ITT) analyses will then be conducted.

OHIP 14 and self-efficacy scores will be the primary outcomes. Initially, we will assess the differences between the interventions and control using 2-sample *t*-tests. The main analysis will be based on linear mixed-effects models for repeated measures (using the OHIP 14 and self-efficacy scores as continuous outcome variables) to assess differences between intervention and control groups. Similar analyses will be conducted for secondary outcome measures. Statistical significance will be set at  $p < .05$ .

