#### **f) Privacy & Confidentiality**

## ORAL HEALTH EDUCATION SENIORS

As in any type of treatment or clinical research program, patients' confidentiality must be carefully guarded and respected. The study will use Protected Health Information (PHI) and a HIPAA Authorization form is being submitted with this application (see Appendix D).

There will be a separate file with identifiers in receipt of the principal investigator. All data with identifying information will be stored in locked files or encrypted, password-protected electronic data storage. Data being analyzed will be identified by subject codes (using the subject identification number) and identifying information will be removed. The identity of patients will not be revealed in the presentation or publication of any results from this project. All assistants and others working on the project will be educated about the importance of strictly respecting patients' rights to privacy and confidentiality and will have completed training concerning proper practice in accordance with HIPAA regulations.

Protected Health Information that will be collected includes the patient's name, date they were seen for the study, phone number, and age. In addition, dental record number, medical and dental chart information related to oral hygiene behaviors and systemic diseases will be accessed from the dental chart for those assigned to intervention group 2. Only those subjects assigned to intervention group 2 will be given the HIPAA Authorization form to sign. The electronic PHI data will be downloaded to a computer using encrypted, password-protected storage of electronic data. All participants will receive a unique random identification number, which will correspond to that person's data. Participant names and corresponding identification numbers will be stored separately in a locked file cabinet or encrypted, password-protected storage of electronic data.

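### Mixed entry types from two sites, with no stated stratification or baseline adjustment, make the OHIP-14 comparisons less precise than they need be

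*Combined protocol and SAP*

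**What the plan says.** Criterion 2 in section 7(b) states that patients "May be new, regular, emergency patients attending the TUKSoD clinic at Kleinlife or clinics at the Dental School". It continues with people "utilizing medical and social services at Kleinlife who have the intention to become patients of record at the dental clinic". So four kinds of entrant, from two sites, are pooled.

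Section 7(d), Study Procedure, says: "This will be a multi-center parallel group study with randomization to one of three arms". On allocation it says: "Randomization will be determined according to a predetermined random sequence". No stratum, block or minimisation factor is named.

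On baseline data, the Measurements part of section 7(d) says: "Demographic Factors Questionnaire will identify key demographic factors such as age, sex, race, ethnicity, education and income level of seniors". The form in Appendix C adds ZIP code. Neither place lists the reason for the visit, patient status or recruiting site. Section 7(f) says that medical and dental chart information "will be accessed from the dental chart for those assigned to intervention group 2", so the chart is not a stated source for the other two arms.

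Under Data Analysis, "demographic variables that differ between groups and are correlated with the primary outcomes will be used as covariates". The main analysis uses "linear mixed-effects models for repeated measures". The plan does not say whether the baseline score is a covariate, a response with means constrained equal across arms, or simply one more response. The group descriptions in section 7(d) provide for baseline forms in all three arms.

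**The concern.** OHIP-14 is a primary outcome, and items 3 and 4 ask about aching and discomfort when eating. A senior who enters through an emergency visit may plausibly score high at baseline and improve once the usual care of any arm has dealt with the problem. A senior attending routinely has less room for such a fall. If so, part of the spread in OHIP-14 change has nothing to do with education, and it widens every contrast on this outcome.

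The stated covariate rule does not reach entry type or site, because neither is a demographic variable on the form. The rule also waits for an observed imbalance before it adjusts for anything. The form of the model matters too. The control arm has only two assessments, at baseline and 12 months. With complete data at two visits, an unconstrained group-by-visit model reproduces the difference in mean change, and that is the analysis in which this noise is fully felt.

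**Working it through.** **The plan's own figure.** The arms add up: 60 + 60 + 70 = 190. Ten of the 70 are calibration patients only, which leaves 180, or 60 per arm. No power, effect size, SD or dropout rate is given, so 190 cannot be reproduced from a power calculation.

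**Inputs.** From the documents: n = 60 per arm, and p < .05 (two-sided assumed). Assumed, because the documents are silent: emergency share p = 0.1 to 0.3; extra natural fall in emergency entrants d = 5 to 10 OHIP-14 points; SD of change within entry type = 8; no dropout.

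**Formulas.**
- 95% range of the chance difference in emergency share between two arms: ±1.96 × √(2p(1−p)/60)
- Resulting shift in the arm contrast: that range × d
- Variance of change, types pooled: 64 + p(1−p)d²
- 95% half-width of an arm contrast: 1.96 × √(2 × variance/60)

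| p, d | Imbalance (points of %) | Shift (OHIP-14 points) | Pooled variance | Share due to type | Half-width, unadjusted | Half-width, adjusted for type |
|---|---|---|---|---|---|---|
| 0.1, 5 | ±10.7 | ±0.54 | 66.25 | 3.4% | 2.91 | 2.86 |
| 0.2, 8 | ±14.3 | ±1.15 | 74.24 | 13.8% | 3.08 | 2.86 |
| 0.3, 10 | ±16.4 | ±1.64 | 85.00 | 24.7% | 3.30 | 2.86 |

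The half-width narrows by 0.05, 0.22 and 0.44 points on a 0-56 scale.

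**The shift and the wider interval are one quantity.** To rounding, 2.86² + 0.54² = 2.91², 2.86² + 1.15² = 3.08² and 2.86² + 1.64² = 3.30². The chance shift is already inside the unadjusted interval and must not be counted as a second harm.

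**What each adjustment recovers.** A simulation took two arms of 60, 6,000 runs per case, a true effect of 0.45 SD, and an emergency elevation of D SD at baseline that has resolved by follow-up. Power was:

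| Baseline/follow-up correlation | p, D | Raw change | Change + entry type | Baseline as covariate | Baseline + entry type |
|---|---|---|---|---|---|
| 0.5 | no emergency entrants | 0.69 | – | 0.80 | – |
| 0.5 | 0.2, 1.0 | 0.62 | 0.68 | 0.79 | 0.81 |
| 0.5 | 0.3, 1.5 | 0.53 | 0.69 | 0.76 | 0.81 |
| 0.7 | no emergency entrants | 0.89 | – | 0.93 | – |
| 0.7 | 0.2, 1.0 | 0.80 | 0.87 | 0.89 | 0.92 |
| 0.7 | 0.3, 1.5 | 0.66 | 0.89 | 0.85 | 0.93 |

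Baseline adjustment alone supplies most of the gain over raw change. Part of that is the ordinary benefit of adjusting for baseline, seen even with no emergency entrants. Entry type then adds 0.02 to 0.05 at correlation 0.5 and 0.03 to 0.08 at 0.7. With no true effect, rejection rates stayed near 5% in all analyses.

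**The case against.** The strongest reply is that broad eligibility is legitimate, stratification is optional in a randomised trial, and the data that matter most are already planned. Baseline OHIP-14 is measured in every arm and would carry much of the acute elevation. This stands, and it puts baseline adjustment first in the remedy. It does not dispose of the point, because the plan never commits to that adjustment.

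Three stronger readings are tempting, and the documents do not support them.
- A reader might infer that an excess of emergency entrants would bias the result towards benefit. Allocation is random, every arm receives usual care, and an excess is as likely in control as in an intervention arm. The standard error already allows for it.
- A reader might infer that the plan cannot detect or correct the problem. Arms can be compared on baseline OHIP-14, and a baseline-adjusted mixed model fits within the stated analysis. The gap is one of specification.
- A reader might infer that site is never logged and that a single unstratified list is used. The documents are only silent: staff would know where they recruited, and strata are neither stated nor excluded.

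The clinical premise is also an assumption. OHIP-14 rates how often impacts occur, not how severe they are now. Items 3 and 4 can move by at most 2 × 4 = 8 points, so a 10-point extra fall needs other items to move as well. No comparable mechanism is evident for self-efficacy.

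**Conclusion.** The point holds as a modest, cheaply avoided loss of precision on OHIP-14. Under the assumed inputs the 95% half-width is 2.9-3.3 points without adjustment against about 2.9 with it. If emergency entrants are few or their extra improvement is small, almost nothing is lost.

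The main gap is that adjustment for baseline is not stated. Recording entry type adds a little beyond that: at a baseline/follow-up correlation of 0.5, power of 0.76-0.79 rises to about 0.81. The size rests wholly on assumed values for the emergency share, the extra fall, the SD and the correlation. The absence of bias and of type I error inflation does not depend on those values; it follows from randomisation.

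**What to change.** Keep eligibility unchanged.

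1. Replace the covariate rule that depends on observed imbalance with prespecified adjustment for the baseline value of each outcome. Enter it as a covariate, or model baseline as a response with means constrained equal across arms. This needs no new data.
2. Record recruiting site (KleinLife or Dental School) and entry type (emergency or other) at consent, in all arms and before allocation.
3. Stratify the random sequence by both, or at least by site.
4. Include both in the mixed models whatever the observed balance. In the self-efficacy model they belong as stratification factors. If baseline is modelled as a response, add their by-visit terms: a main effect alone shifts all of a senior's visits equally and leaves differences in change untouched.

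The cost is two tick-boxes, up to four allocation lists, a few degrees of freedom and slightly uneven arm sizes where strata are small. The emergency-or-other split leaves new, regular and prospective patients together, which limits what it can remove.

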## ORAL HEALTH EDUCATION SENIORS

- 3) Must be able to speak and understand English.
- 4) Must be willing to provide consent to participate in the study for himself/herself.

### **Exclusion criteria:**

#### **Patients:**

- 1) Subjects younger than 55 years old will be excluded from the study.
- 2) Subjects who do not provide consent for participation will be excluded from the study.
- 3) Subjects who do not speak and understand English.

### **c) Study Timelines**

**Table 1: Research Timelines**

Approximate Months/ Year	Goals
March 2017	IRB submission
Summer-Fall 2017	Recruitment, implementation of educational interventions and baseline data collection
Spring Summer 2018	Follow up data collection
Fall 2018	Finalize manuscript for publication

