### **Control Group: (60 seniors).**

Seniors who are randomly assigned to the control group will continue receiving regular dental care under the standard clinic operation. Subjects in this group will complete intake forms to assess main behavioral outcomes, at baseline and after 12 months. No other activities will be conducted in this group.

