### **Intervention Group 1: (60 seniors).**

Seniors who are randomly assigned to the intervention group 1 will continue receiving regular dental care under the standard clinic operation and will be invited to participate in 2 group based education activities over a 12 month period. The sessions will last for 1 hour each time and follow the guidelines established by the Oral Health America Curriculum. Baseline intake forms to assess changes in main behavioral outcomes will be administered before the first education session, after 6 months and after 12 months.

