### **Intervention Group 2: (70 seniors (10 of these are calibration patients exclusively)).**

Seniors who are randomly assigned to the intervention group 2 will continue receiving regular dental care under the standard clinic operation and will also be invited to participate in an individual-based education activity over a 12 month period. The clinic visits will last for 1 hour each time and follow the guidelines established by TUKSoD to provide oral hygiene instruction using a Motivational Interviewing approach. Tailored education will be based on review of health related information to be extracted from medical (systemic diseases), dental chart (oral hygiene behaviors) and patient interview at time of initial examination. Seniors in this group will also receive basic preventative care (dental cleanings, fluoride varnish application (high caries risk individuals only) or referral to a supervised brushing program with high concentration fluoride under the care of the dentist at Kleinlife if needed. All individual based preventative activities will be provided by a Public Health Hygienist, and 3 dental visits will be conducted for subjects in this group during the course of a 18 month period. Baseline intake forms to assess changes in main behavioral outcomes will be administered before the first home based education session, at each follow up visit and after 18 months.

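### Table 1 closes follow-up in Summer 2018, before any 18-month Group 2 form, or the 12-month form of anyone recruited in Fall 2017, can fall due

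*Combined protocol and SAP*

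**What the plan says.** Section 7c, Table 1, gives the trial calendar under a column heading that calls the dates approximate:

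- The calendar opens with submission to the IRB in March 2017.
- The row labelled "Recruitment, implementation of educational interventions and baseline data collection" is dated "Summer-Fall 2017".
- The row labelled "Follow up data collection" is dated "Spring Summer 2018".
- The last row, labelled "Finalize manuscript for publication", is dated Fall 2018. No data collection is listed in this row.

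Section 7d sets the assessments by arm:

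- Control (60 seniors): forms "at baseline and after 12 months".
- Intervention Group 1 (60 seniors): a form before the first session, then "after 6 months and after 12 months".
- Intervention Group 2 (70 seniors, of whom 10 are for calibration only): forms at baseline, at each follow-up visit and at 18 months. The paragraph adds that "3 dental visits will be conducted for subjects in this group during the course of a 18 month period". Its opening sentence, however, gives the individual education activity a 12-month period.

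The abstract gives Group 2 an 18-month period. The Calibration paragraph says that the 10 calibration patients are not part of the study, which leaves 60 in Group 2. Nothing in the protocol extends data collection beyond Summer 2018, and nothing describes the pattern of accrual.

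**The concern.** Table 1 is the only statement of when follow-up opens and closes. A participant whose baseline is in Fall 2017 reaches month 12 in Fall 2018, when the calendar lists only the manuscript. A Group 2 participant reaches month 18 later still.

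OHIP-14 and self-efficacy are the primary outcomes, and the Data Analysis section compares them between arms with mixed models for repeated measures. Staff who kept to the calendar would have to omit the late forms or take them early. Group 2 would then lose its final assessment altogether. Late recruits would lose their 12-month outcome or have it measured short of 12 months.

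**Working it through.** **Inputs.** From Table 1: the baseline window (Summer-Fall 2017) and the follow-up window (Spring-Summer 2018). From section 7d: final forms at 12 months for 60 + 60 = 120 participants, and at 18 months for 70 − 10 = 60. The documents do not define the seasons, so three readings were tried as assumptions.

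**Formula.** Due date = baseline date + 12 or 18 months. A form is late if its due date falls after the last day of Summer 2018. The late shares in the table assume even daily accrual over the baseline window.

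| Season reading | Baseline window | Follow-up closes | 12-month forms due | Late | 18-month forms due | Late |
|---|---|---|---|---|---|---|
| Meteorological | 1 Jun–30 Nov 2017 | 31 Aug 2018 | 1 Jun–30 Nov 2018 | 49.7% | 1 Dec 2018–30 May 2019 | 100% |
| Astronomical | 21 Jun–20 Dec 2017 | 22 Sep 2018 | 21 Jun–20 Dec 2018 | 48.6% | 21 Dec 2018–20 Jun 2019 | 100% |
| Academic | 1 May–31 Dec 2017 | 31 Aug 2018 | 1 May–31 Dec 2018 | 49.8% | 1 Nov 2018–30 Jun 2019 | 100% |

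**18-month forms.** All 60 are late under every reading, and this needs no accrual assumption. The overrun is 1 December 2018 to 30 May 2019 set against 31 August 2018, or 3 to 9 months. The astronomical reading gives the same range; the academic reading gives 2 to 10. For an 18-month form to fall inside the window, baseline would have to be by 28 February 2017 (22 March 2017 on the astronomical reading). That is before, or in the month of, IRB submission. Running collection through Fall 2018 would still leave all 18-month forms late on the first two readings, and about 75% on the academic one.

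**12-month forms.** The overrun is 0 to 3 months (30 November set against 31 August 2018), or up to 4 on the academic reading. The share late equals the share recruited in Fall 2017:

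- even accrual: 120 × 0.486 to 120 × 0.498, or about 58 to 60 of 120;
- one quarter recruited in Fall: 120 × 0.25 = 30;
- three quarters recruited in Fall: 120 × 0.75 = 90;
- at the extremes, none or all 120.

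**If Group 2's last form were at month 12.** The 18-month problem would disappear. The 12-month problem would then apply to 120 + 60 = 180 participants. With even accrual, 180 × 0.486 to 180 × 0.498, or about 88 to 90 final forms, would be late.

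**Follow-up available at the close of the window.** About 15 months for the first recruit and 9 for the last (16 and 8 on the academic reading).

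**The case against.** Table 1 lists approximate goals, while section 7d fixes the assessment times, and nothing tells staff to take forms early or drop them to meet the calendar. A slip of one season at month 12 could fairly be read as approximation. This has force for the 12-month forms, although the next row gives that season to the manuscript. It does not rescue the 18-month forms, which overrun by several months.

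The Group 2 paragraph is also inconsistent with itself, because it gives 12 months for the education activity. This stands as a condition on the 18-month part. The form schedule and the visit period in the same paragraph both say 18 months, as does the abstract, so the 18-month form is in the current text.

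A reader might infer more than the documents support:

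- *Half of the 12-month forms fall outside the calendar.* This holds only with even accrual, and the protocol gives no accrual pattern.
- *Follow-up in Spring 2018 means that 12-month forms are taken early.* Group 1 has a 6-month form and Group 2 has forms at its visits. For a September-November recruit, the 6-month form falls due in March-May 2018, inside that row.
- *The calendar causes unequal follow-up between all arms.* Control and Group 1 share the recruitment window and the 12-month endpoint, so a cut-off would act on their 12-month forms alike. The 12 against 18 month difference for Group 2 lies in the arm descriptions and would remain after Table 1 was corrected.

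**Conclusion.** The calendar and the assessment schedule contradict each other. If the 18-month form stands, all 60 final Group 2 forms fall due about 3 to 9 months after follow-up closes, regardless of accrual and with only minor dependence on how the seasons are dated. The 12-month forms of everyone recruited in Fall 2017 fall due up to about 3 months late. The number affected is not known: about half with even accrual, and 25% to 75% if one quarter to three quarters enrol in Fall.

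Harm to the comparison follows only if the calendar is enforced, which the documents neither require nor rule out. This should be corrected before recruitment. It does not show that the design is unworkable. It also does not settle which time point the arms should be compared at, because the Group 2 paragraph schedules no explicit month-12 form.

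**What to change.** Reconcile Table 1 with the three arm descriptions in section 7d, and resolve the 12 against 18 month wording within the Group 2 paragraph. Then:

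- Set the end of follow-up from the last recruit's final scheduled assessment. On the stated recruitment window this is about the end of Fall 2018 if month 12 is the last assessment in every arm, or about mid-2019 if the 18-month form is kept.
- Place analysis and manuscript after that date.
- State that each form is timed from the participant's own baseline, and that none is taken early or dropped to meet the calendar.

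The cost is a later end date and some protocol wording, with no extra participants. The choice of a common time point for the arm comparison should be handled separately, since it may require a Group 2 assessment that is not now scheduled.
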